#### **11.4 Key variables**

Reference standard: disease status of a lesion will be defined by biopsy of suspicious lesions, when clinically feasible. 12-months clinical follow-up with imaging will be gold standard if biopsy cannot be done.

Test to be evaluated:  $^{68}\text{Ga}$ -NeoBOMB1 and  $^{68}\text{Ga}$ -PSMA R2 positivity will be determined by the operator as uptake more than the adjacent background (malignant) or less (benign). Visual conspicuity against background on the diffusion weighted images and presence of an anatomically corresponding abnormality on the T1w and T2w images are the criteria for detecting a lesion on MRI.

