##### **11.4.1 Analysis Population**

All lesions identified by  $^{68}\text{Ga}$ -NeoBOMB1 PET/MRI and  $^{68}\text{Ga}$ -PSMA R2 PET/MRI.

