##### **11.4.2 Analysis Plan**

- Sensitivity, specificity, and positive and negative predictive value of imaging modalities will be estimated.
- Sensitivity and specificity of PET/MRI and MR alone will be compared by McNemar tests of paired proportions.
- The number and type of discrepancies between  $^{68}\text{Ga}$ -NeoBOMB1 and  $^{68}\text{Ga}$ -PSMA R2 will be tabulated.
- We will explore hypotheses about the reasons for such discrepancies, such as PSA level/velocity, Gleason score, and location.

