#### **11.5 Sample size justification**

The following estimate is for a per-lesion analysis. We expect approximately 70% of patients (~35) to have one or more PET-positive findings and approximately 1/3 to be biopsied. Our existing data for  $^{68}\text{Ga}$  PSMA-11 and  $^{68}\text{Ga}$ -RM2 (please see attached publications) indicate no false positive findings based on biopsy. We cannot predict an average number of lesions per patient given small data available to date, but if only half of the positive patients have more than one lesion, this will easily yield 50 lesions. We also expect the sensitivity of MR alone to be roughly 40%, while that of PET to be roughly 60% or more. A sample size of 50 patients will provide 90% power at one-sided 5% error to detect such a difference. Participants who complete only one PET/MRI scan (either due to withdrawal of consent or loss to follow-up) will not be replaced with additional subjects.

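### Section 11.5 gives an unconditional 90% power, but the power of the planned McNemar test depends on a PET-versus-MR discordance that the text does not state; at 40% vs 60% with 50 lesions, 90% holds only up to about 24–28% discordance

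*Combined protocol and SAP*

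**What the plan says.** All references are to the combined protocol and SAP.

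- **Unit.** Section 11.5 opens with "The following estimate is for a per-lesion analysis". It expects about 70% of patients (about 35) to have a PET-positive finding and about a third to be biopsied. It adds that "if only half of the positive patients have more than one lesion, this will easily yield 50 lesions".
- **Effect.** "We also expect the sensitivity of MR alone to be roughly 40%, while that of PET to be roughly 60% or more".
- **Power.** "A sample size of 50 patients will provide 90% power at one-sided 5% error to detect such a difference".
- **Test.** Section 11.4.2: "Sensitivity and specificity of PET/MRI and MR alone will be compared by McNemar tests of paired proportions". The version (exact, mid-p, uncorrected or continuity-corrected) is not named.
- **Analysis set.** Section 11.4.1 takes "All lesions identified by" the two PET/MRI scans.
- **Not stated.** There is no PET-versus-MR discordance, power formula, number of reference-positive lesions, or allowance for several lesions in one patient. The one agreement figure, in Section 11.3 (two thirds the same, one third different), compares tracer with tracer and not PET with MR.

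**The concern.** In a paired comparison, the two sensitivities do not determine the power. McNemar's test uses only the lesions on which the methods disagree. The same 20-point difference is easy to detect when nearly everything MR finds is also found on PET, and much harder when each method finds many lesions the other misses. A single figure of 90% hides which case was assumed.

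Two further gaps make the figure hard to interpret. The paragraph starts with lesions and ends with patients, and the denominator of a sensitivity (reference-positive lesions) is never counted. Also, about 50 lesions would come from about 35 patients, and lesions in one patient may behave alike.

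This is the only power statement in the documents, and it supports the comparison with MR alone that Section 10.1 names as the principal goal. At the planning floor, the chance of missing a true 20-point gain ranges from a few per cent to over 40%, depending on an input the reader cannot see.

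**Working it through.** **Inputs.** From Section 11.5: MR sensitivity 0.40, PET 0.60 (the floor), one-sided 5%, 50 lesions. From Section 11.4.2: McNemar. Assumed, because not given: discordance ψ, independence of lesions, and all 50 lesions being reference-positive.

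**Can the stated 90% be reproduced?** Not for McNemar, because ψ is missing. Of the calculations tried that need no ψ:
- One-sample normal test of 60% against a fixed 40%: Φ(0.20·√50/√0.24 − 1.645) = 89.3%.
- Exact one-sample rule (at least 27 of 50): 84.4%, with a type I error of 3.1%.
- Two independent groups of 50: 64.1%.

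Only the first lands near 90% at the stated error rate. It ignores the sampling error of MR and is not the planned test.

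**Possible range of ψ.** Let b be the share of lesions seen on PET only and c the share seen on MR only. Then b − c = 0.20 and b + c = ψ, so b = (ψ + 0.20)/2.
- Minimum ψ = 0.20, when every MR-detected lesion is also PET-detected.
- Independent detections: ψ = 0.60·0.60 + 0.40·0.40 = 0.52.
- Share of MR-detected lesions also seen on PET = (0.60 − b)/0.40. At ψ = 0.25, b = 0.225 and the share is 0.375/0.40 = 94%.

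**Power of the planned test.** Asymptotic formula, with d = 0.20 and n = 50:

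Power = Φ[(d√n − 1.645√ψ)/√(ψ − d²)]

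- ψ = 0.25: (1.414 − 0.822)/0.458 = 1.29, giving 90.2%.
- ψ = 0.40: (1.414 − 1.040)/0.600 = 0.62, giving 73.3%.

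The other columns enumerate all outcomes for each version of the test.

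| ψ | MR lesions also on PET | Formula | Exact | Mid-p | Uncorrected |
|---|---|---|---|---|---|
| 20% | 100% | 95.5% | 98.2% | 99.4% | 99.9% |
| 25% | 94% | 90.2% | 88.4% | 92.9% | 94.2% |
| 30% | 87.5% | 84.3% | 80.7% | 86.6% | 87.2% |
| 40% | 75% | 73.3% | 67.9% | 74.5% | 74.5% |
| 52% | 60% | 62.9% | 56.6% | 63.4% | 63.4% |
| Largest ψ with 90% | | 25.1% | 24.1% | 27.3% | 28.0% |

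**What raises power.**
- PET 65% (d = 0.25, n = 50): 90% holds to ψ = 39% by the formula.
- PET 70% (d = 0.30) with independent detections (ψ = 0.54): 91% by the formula, 89% exact.
- More reference-positive lesions: if the 50 are PET-positive and all true, the total could be 50/0.60 = 83. At 40% vs 60%, 83 lesions hold 90% to ψ of about 40% (formula) or 38% (exact).

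**What lowers power.** As an illustration, take 17.5 patients with one lesion and 17.5 with two, so 52.5 lesions. The size-weighted mean cluster size is (17.5·1 + 17.5·4)/52.5 = 1.67, and the design effect is 1 + 0.67ρ, where ρ is an assumed within-patient correlation of the PET-minus-MR difference. By the formula:

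| ρ | Effective n | Power, ψ = 25% | Power, ψ = 30% |
|---|---|---|---|
| 0 | 52.5 | 91% | 86% |
| 0.1 | 49.2 | 90% | 84% |
| 0.3 | 43.75 | 86% | 80% |

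**The case against.** The sponsor has good answers to part of this.

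- **The inputs are at their least favourable.** Section 11.5 allows PET sensitivity above 60%, and its 50 lesions come from PET-positive patients. With the premise that existing data "indicate no false positive findings based on biopsy", the reference-positive total could be larger than 50. Either change lifts the 24–28% limit. This stands, so the threshold belongs only to the stated floor.
- **Near-nesting is plausible.** PET/MRI contains an MR component. But Section 10.2 has MR read blinded to PET, and Section 11.4 bases tracer positivity on uptake, so nesting is not guaranteed.
- **The choice of test matters.** The uncorrected test has 94% power at 25% discordance and 87% at 30%, above the asymptotic formula. The formula's values should therefore not be presented as upper limits.
- **The units are linked.** Section 11.5 does lead from 50 patients to about 35 positive ones to 50 lesions. What remains missing is the number of reference-positive lesions.
- **The clustering loss is assumed.** No correlation is given, and at 0.1 the loss is only one or two points.
- **The publications that Section 11.5 says are attached are not available here.** They may hold paired PET and MR data, so the gap is established only for the text at hand.

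A reader might infer that the PET-only analysis set in Section 11.4.1 further reduces power. It does not. Restricting the test to 50 such lesions, with a second tracer assumed independent at 60%, gives 94–98% by the formula (92% to over 99% exact) across the same discordances. That set favours PET by construction, which is a question of bias.

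**Conclusion.** The concern holds as a conditional statement. For the planned McNemar test, the flat 90% cannot be reproduced from the plan's stated inputs. At 40% vs 60%, one-sided 5% and 50 independent reference-positive lesions, it is met only up to about 24% (exact), 25% (asymptotic formula), 27% (mid-p) or 28% (uncorrected) discordance. Beyond that, power falls to 81–87% at 30%, 68–75% at 40% and 57–63% with independent detections. Discordance, within-patient correlation and PET values above 60% are assumptions here, shown as ranges.

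Two stronger readings are tempting but unsupported. One is that 90% is impossible or that the trial is underpowered: near-nesting, a PET sensitivity of 65–70%, or about 83 reference-positive lesions could each deliver about 90% or more. The other is that the sponsor used a one-sample test: 89.3% is close to the stated figure, but the documents do not say how it was obtained.

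**What to change.** Keep 50 participants, the McNemar test and the planning sensitivities. In Section 11.5:

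1. Name the lesion as the unit of analysis.
2. Name the McNemar version.
3. State the expected number of reference-positive lesions and the assumed PET-versus-MR discordance, with its source.
4. Replace the flat 90% with power for that version over a range. For 50 independent reference-positive lesions at 40% vs 60% and one-sided 5%, discordance from 20% to 40% gives 98% down to 68% (exact), or over 99% down to 75% (uncorrected).
5. Say that positive within-patient correlation of the PET-minus-MR difference would reduce these figures, and that higher PET sensitivity or more reference-positive lesions would raise them. Do not call the figures upper limits.

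Separately, reconcile the sensitivity denominator with Section 11.4.1. A set limited to PET/MRI-identified lesions leaves out those seen only on MR or missed by PET, and so favours PET. The sensitivity comparison should use all reference-positive lesions identified by either PET/MRI, by MR or by follow-up.

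Cost: a rewritten paragraph in Section 11.5 and a clarified denominator, with no extra participants and no change of test. The downside is that the stated power becomes conditional and less favourable.

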#### **11.6 Accrual estimates**

We expect the accrual of 50 patients over 24 months. There are approximately 10 prostate cancer patients scanned each week in Nuclear Medicine to evaluate for metastatic disease. We plan to enroll 50 participants over 24 months and this is achievable given our experience with other protocols and the expected support from the referring physicians, Drs [name], [name], and [name].

### **Inclusion/Exclusion Criteria Checklist**

Protocol Title:	68Ga NeOBOMB1 and 68Ga-PSMA R2 PET/MRI PET/MRI in Patients with Biochemically Recurrent Prostate Cancer		
Protocol Number:	46258		
Principal Investigator:	[name]		

Inclusion Criteria – Yes must be checked to be eligible (From IRB approved protocol)	Yes	No	Supporting Documentation
1. Biopsy proven prostate adenocarcinoma			
2. Rising PSA after definitive therapy with prostatectomy or radiation therapy (external beam or brachytherapy)			
a. Post radical prostatectomy (RP)			
i. PSA greater than 0.2 ng/mL measured after at least 6 weeks from radical prostatectomy			
ii. Confirmatory persistent PSA greater than 0.2 ng/mL (total of two PSA measurements greater than 0.2 ng/mL)			
b. Post-radiation therapy			
i. A rise of PSA measurement of 2 or more ng/mL over the nadir			
3. Able to provide written consent			
4. Karnofsky performance status of $\geq 50$ (or ECOG/WHO equivalent)			

Exclusion Criteria – No must be checked to be eligible (From IRB approved protocol)	Yes	No	Supporting Documentation
1. Patient is $< 18$ years old at the time of the drug administration			
2. Inability to lie still for the entire imaging time			
3. Inability to complete the needed investigational and standard-of-care imaging examinations due to other reasons (severe claustrophobia radiation phobia, etc.)			
4. Any additional medical condition, serious intercurrent illness, or other extenuating circumstance that, in the opinion of the Investigator, may significantly interfere with study compliance.			
5. Metallic implants (contraindicated for MRI)			
6. Known allergy, hypersensitivity, or intolerance to the investigational product or its excipients.			

\*All subject files must include supporting documentation to confirm subject eligibility. The method of confirmation can include, but is not limited to, laboratory test results, radiology test results, subject self-report, and medical record review.

